Study Information

Title	Observational Study of Effectiveness and Safety of Recombinant Zoster Vaccine (Shingrix) [®] in Moderately-to-Severely Active Ulcerative Colitis (UC) or Rheumatoid Arthritis (RA) Patients Treated with Tofacitinib (Xeljanz) [®] in Real-World Clinical Care Settings
Protocol number	A3921427
Protocol version identifier	Version 2.1
Date	05 October 2023
EU Post Authorization Study (PAS) register number	EUPAS48998
Active substance	Tofacitinib (ATC code: LD4AA29)
Medicinal product	Xeljanz [®] (tofacitinib)
Research question and objectives	
The research questions are the following:
 
 • In patients with moderately to severely active UC or RA receiving ongoing treatment with tofacitinib, what is the incidence rate of HZ in those administered RZV (Shingrix)[®] compared with those not administered the vaccine? • In patients with moderately to severely active UC or RA receiving ongoing treatment with tofacitinib, does the incidence rate of UC or RA disease flares differ in those who are administered RZV compared with those not administered the vaccine? 
The primary objective for effectiveness in this study is:
 
 • To estimate and compare the incidence rate of HZ among patients with UC or RA being treated with tofacitinib who receive two doses of RZV relative to the incidence rate

PFIZER CONFIDENTIAL

	
among patients with UC or RA being treated with tofacitinib who do not receive RZV.
 
The secondary objective for effectiveness in this study is:
 
 To estimate and compare the incidence rate of HZ among patients with UC or RA being treated with tofacitinib who receive at least one dose of RZV relative to the incidence rate among patients with UC or RA being treated with tofacitinib who do not receive RZV. 
The secondary objectives for safety in this study are:
 
 To estimate and compare the incidence rate of UC disease flares among patients with UC being treated with tofacitinib who receive at least one dose of RZV relative to the incidence rate among patients with UC being treated with tofacitinib who do not receive RZV. To estimate and compare the incidence rate of RA disease flares among patients with RA being treated with tofacitinib who receive at least one dose of RZV relative to the incidence rate among patients with RA being treated with tofacitinib who do not receive RZV.

2. LIST OF ABBREVIATIONS

Abbreviation	Definition
AHFS	American Hospital Formulary Service
ATT	Average Treatment Effect in the Treated
COVID-19	Coronavirus Disease 19
CPT®	Current Procedural Terminology
csDMARD	Conventional Synthetic Disease-modifying Antirheumatic Drug
ENCePP	European Medicines Agency, European Network of Centres for Pharmacoepidemiology and
FDA	Food and Drug Administration
HCPCS	Healthcare Common Procedure Coding System
HIV	Human Immunodeficiency Virus
HZ	Herpes Zoster
IBD	Inflammatory Bowel Disease
ICD-10	International Classification of Diseases, 10 th Revision
IEC	Independent Ethics Committee
IPTW	Inverse Probability of Treatment Weight
IRB	Institutional Review Board
ISPE	International Society of Pharmacoepidemiology
JAK	Janus Kinase
MA-PD	Medicare Advantage and Medicare Part D
NDC	National Drug Code
ORD	Optum Research Database
PASS	Post-Authorisation Safety Study
PPV	Positive Predictive Value
RA	Rheumatoid Arthritis
RWD	Real-world Data
RWE	Real-world Evidence
RZV	Recombinant Zoster Vaccine
SAP	Statistical Analysis Plan
SAS	Statistical Analysis System
SD	Standardized Difference
SOPs	Standard Operations Procedures
TNF	Tumor Necrosis Factor
UC	Ulcerative Colitis
US	United States

4. ABSTRACT

In [Annex 1](#) as stand-alone document.

5. AMENDMENTS AND UPDATES

Amendment number	Date	Protocol section(s) changed	Summary of amendment(s)	Reason
1	16 May 2023	Throughout the protocol	Updated the order to “effectiveness and safety” from the previous order “safety and effectiveness” Updated study time period units in months to days, such as 365 days instead of 12 months	The order was updated to better reflect the primary and secondary objectives of this study and PMC 3400-6 Time period units in “months” were updated to “days” to be more consistent, as calendar months have varying length in days
		Title Page	Updated objectives to align with changes in protocol Updated protocol author and contact information	Editorial change Study transition for the protocol author
		Section 2	Updated to include new abbreviations	Editorial change
		Section 3	Updated contact information for a principal investigator of the protocol	Study transition for the principal investigator
		Section 4	Revised version, date, and author Updated objectives, eligibility criteria, cohorts, and follow-up to reflect the 2-dose analysis as the primary objective	Editorial change and study transition The abstract was updated based on updates in the protocol, which was updated in response to the FDA feedback (dated 03 February 2023) on protocol version 1.0
		Section 6	Updated milestone dates	Project timelines have changed due to this protocol amendment in response to the FDA feedback (dated 03 February 2023) on protocol version 1.0

Amendment number	Date	Protocol section(s) changed	Summary of amendment(s)	Reason
		Section 7	Added text and citation on the recommended dosing schedule of RZV	Editorial changes to add the dosing schedule in the background section
		Section 8	Changed study objectives such that assessment of the 2-dose regimen is the primary objective.	This change was made in response to request by the FDA in their feedback on protocol version 1.0.
		Section 9.1	Addition of cohorts to correspond to revised study objectives. Extension of study period end date from 31 December 2022 to 31 July 2023 (or most recent available data at the time the data are extracted).	This change was made in response to request by the FDA in their feedback on protocol version 1.0, Study period extended due to later start of data collection.
		Section 9.2	Updated the study population, specifically the eligibility criteria (Section 9.2.1 and 9.2.2), exposure and comparator cohort definitions (Section 9.2.3.2), baseline period definition (Section 9.2.4), and follow-up period definitions (Section 9.2.5) to correspond to revised study objectives.	This change was made in response to request by the FDA in their feedback on protocol version 1.0 (dated 03 February 2023), which requested the 2-dose RZV analysis to be the primary objective.
		Section 9.3.4	Updated definitions to distinguish RZV doses using claims codes	This change was made in response to request by the FDA in their feedback on protocol version 1.0.
		Section 9.3.5.2	Removed biologics (TNF and non-TNF) from the list of medications considered as part of the definition for UC disease flare	Upon further review of the literature, most studies using claim-based indicators to capture UC or RA disease flares did not include biologics as part of their algorithms ^{18,20,23} . Only one study included biologic as a predictor of UC disease flare ¹⁹ , but when evaluated as a single indicator, biologic was not a statistically significant positive predictor of UC flare. Thus, biologics

Amendment number	Date	Protocol section(s) changed	Summary of amendment(s)	Reason
				were removed from the medications considered for UC disease flare in the secondary objective, and also to be consistent with the definition for RA disease flare. Biologics will be explored as part of the disease flare definition in sensitivity analysis (Section 9.7.4)
		Section 9.4.2	Updated abbreviated name for database to full name	Editorial change
		Section 9.5	Updated study size using the most recently available data	Updated preliminary patient counts based on the most recent data
		Section 9.7	Updated data analysis (propensity score modeling in Section 9.7.1, IPTW in Section 9.7.2) to correspond to revised study objectives including separate propensity score models for 2-dose and ≥ 1 dose analyses and subgroup analyses. Updated text in Section 9.7.3 to reflect the 2-dose analysis as the primary analysis	This change was made in response to request by the FDA in their feedback on protocol version 1.0.
		Section 9.7.4	Added sensitivity analyses to 1) examine recent tofacitinib users (discontinuation within specified time period) in addition to current tofacitinib users, and 2) explore alternative definitions of disease flare, including more expansive definitions that consider other medications of interest, such as biologics and other JAK inhibitors	Sensitivity analysis on recent tofacitinib users was added to evaluate across a range of real-world use patterns and address the potential for extended immunosuppressant effects of tofacitinib following discontinuation. Sensitivity analysis on alternative definitions of disease flare was added to evaluate potential misclassification of outcome.
		Section 9.9	Added study limitation regarding 1) potential misclassification of RZV dose, and 2) potential misclassification of disease flare	Limitations were added to address study limitations when using claims data

PFIZER CONFIDENTIAL

CT24-WI-GL02-RF02 4.0 Non-Interventional Study Protocol Template For Secondary Data Collection Study

01-Jun-2022

Page 10 of 96

Amendment number	Date	Protocol section(s) changed	Summary of amendment(s)	Reason
2	05 October 2023	Section 9.2.2	Updated exclusion criterion to clarify that patients with a diagnosis code for HZ infection on the cohort entry date (Day 0) will not be excluded from the study	This clarification was made to align the exclusion criterion with Figure 2(a) in response to the FDA feedback on protocol version 2.0 (letter dated 30 June 2023).
		Section 9.3.5.1	Added text to clarify the operational definition of HZ infection	This update was made to provide justification and clarity in response to the FDA feedback on protocol version 2.0 (letter dated 30 June 2023).
		Section 9.3.6.4	Added a variable for number of UC/RA treatments during the baseline period to the list of covariates	This variable was added to enhance capture of disease severity.

6. MILESTONES

Milestone	Planned date
Start of data collection	02 January 2024
End of data collection	14 September 2024
Registration in the EU PAS register	Pending (prior to start of data collection)
Final study report*	14 September 2025

*Anticipated to include data from 20 October 2017 to 31 July 2023 (or most recent available data at the time the data are extracted)

7. RATIONALE AND BACKGROUND

Tofacitinib (Xeljanz[®], Pfizer Inc., New York, NY) is an oral Janus kinase (JAK) inhibitor with multiple indications, including for individuals with moderately to severely active ulcerative colitis (UC) or rheumatoid arthritis (RA) who have had an inadequate response or intolerance to one or more tumor necrosis factor (TNF) blockers. UC, a type of inflammatory bowel disease (IBD), is an autoimmune condition involving chronic inflammation of the mucosa of the rectum and colon, clinically characterized by bloody diarrhea and abdominal pain.¹ Rheumatoid arthritis (RA) is an autoimmune condition involving chronic localized and systemic inflammation, with inflammation of the joints leading to erosion or destruction of joint structures, affecting function, and leading to progressive disability.² Patients who have UC or RA are at increased risk of infections, including herpes zoster (HZ), due to the underlying autoimmune condition, and also as a consequence of treatment with immunosuppressant therapies.^{3,4} Increased rates of HZ have been observed in patients treated with tofacitinib compared to patients receiving placebo.^{5,6} Consequently, HZ is among the infections included in the Warnings section in the prescribing information for tofacitinib.⁷

Shingrix[®], a recombinant zoster vaccine (RZV), was approved in the United States (US) in October 2017 for the prevention of HZ infection in adults 50 years and older who are immunocompetent. It was subsequently approved (July 2021) for use in adults 18 years and older who are or will be at increased risk of HZ due to immunodeficiency or immunosuppression caused by known disease or therapy. In adults with weakened immune systems, RZV was between 68% and 91% effective in preventing HZ, depending on their underlying immunocompromising condition.⁸ RZV is a 2 dose vaccine; it is recommended that the second RZV dose be given 2 – 6 months after the first, or 1 – 2 months after the first if needed among people with weakened immune systems.⁹

Given the immunosuppressive effects of tofacitinib, which provide a foundation for clinical benefit in treating patients with UC or RA, there is concern that RZV administered to patients receiving ongoing treatment with tofacitinib may be less effective in preventing HZ. Additionally, as RZV is an adjuvanted vaccine, there has been question as to whether it could induce flares in patients with UC or RA.^{10,11} Given these concerns along with the recently

expanded indication for use of RZV, a study to assess the real-world effectiveness and safety of RZV in this population is to be conducted. This is a post-approval effectiveness and safety study in which Optum proposes to utilize real-world data (RWD) in accordance with US Food and Drug Administration (FDA) guidance for industry about the use of real-world evidence (RWE) to help support post-approval study requirements.^{12,13} This study presents a valuable opportunity to use RWD since RZV is approved for use in immunocompromised adults 18 years and older and is the current standard of care.⁸

This non-interventional study is designated as a Post-Authorisation Safety Study (PASS) and is a post-marketing commitment to the United States (US) (FDA).

8. RESEARCH QUESTION AND OBJECTIVES

The research questions are the following:

1. In patients with moderately to severely active UC or RA receiving ongoing treatment with tofacitinib, what is the incidence rate of HZ in those administered RZV (Shingrix[®]) compared with those not administered the vaccine?
2. In patients with moderately to severely active UC or RA receiving ongoing treatment with tofacitinib, does the incidence rate of UC or RA disease flares differ in those who are administered RZV compared with those not administered the vaccine?

The primary objective for effectiveness in this study is:

- To estimate and compare the incidence rate of HZ among patients with UC or RA being treated with tofacitinib who receive two doses of RZV (between 1 and 6 months apart as specified in Section 9.2.3.2.1.1) relative to the incidence rate among patients with UC or RA being treated with tofacitinib who do not receive RZV.

The secondary objective for effectiveness in this study is:

- To estimate and compare the incidence rate of HZ among patients with UC or RA being treated with tofacitinib who receive at least one dose of RZV relative to the incidence rate among patients with UC or RA being treated with tofacitinib who do not receive RZV.

The secondary objectives for safety in this study are

1. To estimate and compare the incidence rate of UC disease flares among patients with UC being treated with tofacitinib who receive at least one dose of RZV relative to the incidence rate among patients with UC being treated with tofacitinib who do not receive RZV.
2. To estimate and compare the incidence rate of RA disease flares among patients with RA being treated with tofacitinib who receive at least one dose of RZV relative to the incidence rate among patients with RA being treated with tofacitinib who do not receive RZV.

PFIZER CONFIDENTIAL

CT24-WI-GL02-RF02 4.0 Non-Interventional Study Protocol Template For Secondary Data Collection Study

01-Jun-2022

Page 13 of 96

9. RESEARCH METHODS

9.1. Study Design

This is a non-interventional observational cohort study to evaluate the effectiveness and safety of RZV in real-world patients with UC or RA receiving ongoing treatment with tofacitinib. As claims data typically have data lags due to the delay between the occurrence of a health service, claim adjudication, until data availability, adult patients 18 years and older with UC or RA treated with tofacitinib between 20 October 2017 (the date of RZV approval in the US) and 31 July 2023 (or most recent available data at the time the data are extracted) will be identified.

Based on diagnosis of UC or RA and receipt of RZV, patients who are current users of tofacitinib (defined in Section 9.2.3.1) will be classified into the following 8 exposure cohorts, as illustrated by [Figure 1](#).

[figure not shown]
Cohorts for the primary objective (effectiveness):

1. UC RZV 2-Dose: UC patients who receive two doses of RZV;
2. UC Comparator 2-Dose: UC patients who do not receive RZV and are time-matched (within a 4-week window) to patients in the UC RZV 2-Dose cohort;
3. RA RZV 2-Dose: RA patients who receive two doses of RZV;
4. RA Comparator 2-Dose: RA patients who do not receive RZV and are time-matched (within a 4-week window) to patients in the RA RZV 2-Dose cohort;

Cohorts for the secondary objectives (effectiveness and safety):

5. UC RZV ≥ 1 Dose: UC patients who receive at least one dose of RZV;
6. UC Comparator ≥ 1 Dose: UC patients who do not receive RZV and are time-matched (within a 4-week window) to patients in the UC RZV ≥ 1 Dose cohort;
7. RA RZV ≥ 1 Dose: RA patients who receive at least one dose of RZV; and
8. RA Comparator ≥ 1 Dose: RA patients who do not receive RZV and are time-matched (within a 4-week window) to patients in the RA RZV ≥ 1 Dose cohort.

Figure 1. Study Design

To assess the effectiveness of RZV among patients treated with tofacitinib, the primary outcome for this study is the occurrence of new HZ infection. Occurrences of new HZ infection will be identified by the presence of a diagnostic code in claims for HZ infection after the second dose of RZV in the primary objective and after the first dose of RZV in the secondary objective. To assess the safety of RZV among patients treated with tofacitinib, the secondary outcome for this study is disease flare after the first dose of RZV: UC flare within the UC cohorts and RA flare within the RA cohorts. Occurrences of disease flare will be defined based on claims-based indicators and informed by review of the published literature.

Propensity scores that discriminate between receipt and non-receipt of RZV will be created from a wide variety of baseline demographic, comorbidity, disease severity (based on proxies for disease severity, such as treatment with advanced therapy), and comedication indicators, as well as risk factors for HZ. The propensity scores will be used to calculate inverse probability of treatment weights (IPTWs) to adjust for potential confounding in the comparative analysis. The main analysis for this project will estimate the incidence of the primary and secondary outcomes within the weighted cohorts, comparing those with RZV receipt to those without RZV receipt, yielding estimates of RZV effectiveness (primary and secondary outcomes) and safety (secondary outcomes) in those treated with tofacitinib. The main comparison will be among the subgroup of patients whose treatment with tofacitinib overlaps with both doses of RZV relative to patients treated with tofacitinib who do not receive RZV, as sample size allows. All analyses will be performed separately within the UC and RA cohorts.

9.2. Setting

The source population will consist of adult patients 18 years and older treated with tofacitinib with moderately to severely active UC or RA between 20 October 2017 (the date

of RZV approval in the US) and 31 July 2023 (or most recent available data at the time the data are extracted). Severity of UC and RA will not be measured directly; rather, it will be assumed based on the indications for tofacitinib treatment.⁷ Exposure to tofacitinib will be identified as described in Section 9.2.3.1.

9.2.1. Inclusion Criteria

Patients must meet all of the following inclusion criteria at the time of cohort entry (defined as the second qualifying RZV administration date in Section 9.2.3.2.1.1 for the RZV 2-Dose analysis, and as the first qualifying RZV administration date in Section 9.2.3.2.2.1 for the RZV ≥ 1 Dose analysis) to be eligible for inclusion in the study:

1. Aged 18 years of age or older;
2. Have complete medical coverage and pharmacy benefits (ie, eligible to receive complete reimbursement, minus applicable co-pays, for physician, hospital, and prescription drug services) and have at least 365 days of continuous health plan enrollment prior to and including cohort entry date;
 - Patients in the RZV 2-Dose analysis will also be required to have complete medical coverage and pharmacy benefits and continuous health plan enrollment during the 28 days after cohort entry date, as the follow up time will be assessed from day 29 after cohort entry date (Section 9.2.5.1);
3. Identified as a current user of tofacitinib; and
4. Have a diagnosis of UC or RA in the 365 days prior to and including the cohort entry date.

9.2.2. Exclusion Criteria

Patients meeting any of the following criteria will not be included in the study:

1. Receipt of RZV (comparator cohorts only in the RZV 2-Dose analysis) during the 365 days prior to cohort entry, excluding the cohort entry date;
2. Diagnosis of HZ infection in the 365 days prior to cohort entry, excluding the cohort entry date;
 - Presence of a diagnosis code for HZ infection on the same date as RZV receipt (Dose 1 or Dose 2) will not be cause for exclusion from the study due to the administrative claims process;
3. Receipt of a solid organ transplant or hematopoietic stem cell transplant during the 365 days prior to cohort entry, excluding the cohort entry date;

4. In addition, patients with any of the following claims-based indicators of disease flare during the 91 days prior to cohort entry (as described in Section 9.2.3.2.1 for the RZV 2-Dose analysis, and in Section 9.2.3.2.2 for RZV ≥ 1 Dose analysis) will not be included in the study:
- Emergency room visit or hospitalization with UC as primary diagnosis (UC cohorts);
 - UC-related surgery (ie, colectomy, proctocolectomy) (UC cohorts); and
 - Emergency room visit or hospitalization with RA as primary diagnosis (RA cohorts).

[figure not shown]
In addition, patients meeting any of the following criteria will not be included in the RZV 2- Dose analysis:

5. Diagnosis of HZ infection within 28 days after but not including the cohort entry date (ie, Days [1,28]), as the follow up time will be assessed from day 29 after cohort entry date (Section 9.2.5.1); and
6. Occurrence of any censoring event (ie, disenrollment from health plan, death, end of the study period, or receipt of RZV) within 28 days after cohort entry date (Section 9.2.5.1).

Figure 2 summarizes the schematic for assessing patient eligibility, as well as assessment of covariates and outcomes, for (a) the RZV 2-Dose analysis and (b) the RZV ≥ 1 Dose analysis, with details outlined in the subsequent sections.

Figure 2. Schematic for Assessing Eligibility, Covariates, and Outcomes of RZV Initiators and Comparators in (a) RZV 2-Dose Analysis and (b) RZV ≥ 1 Dose Analysis

(a)

- a. Up to 32 day gaps in medical or pharmacy enrollment allowed
- b. Receipt of RZV exclusion applied to Comparator cohorts only
- c. Baseline conditions included: healthcare utilization, comorbid conditions, and treatment history
- d. Earliest of: outcome of interest (HZ), disenrollment, death, end of the study period, or receipt of RZV (comparator cohorts only)

[figure not shown]
PFIZER CONFIDENTIAL

CT24-WI-GL02-RF02 4.0 Non-Interventional Study Protocol Template For Secondary Data Collection Study

01-Jun-2022

Page 18 of 96

(b)

- a. Up to 32 day gaps in medical or pharmacy enrollment allowed
- b. Baseline conditions included: healthcare utilization, comorbid conditions, and treatment history
- c. Earliest of: outcome of interest (HZ), disenrollment, death, end of the study period, or receipt of RZV (comparator cohorts only)
- d. Earliest of: outcome of interest (disease flare), disenrollment, death, end of the study period, receipt of RZV (comparator cohorts only), or 90 days of follow-up

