 Non-tofacitinib exposed person-time
★ First RZV administration
★ Second RZV administration

[figure not shown]
9.2.3.2.1.2. Comparator 2-Dose Cohorts

In a similar fashion to the identification of the RZV 2-Dose cohorts, Optum will identify a cohort of patients without exposure to RZV among patients who are current users of tofacitinib. To minimize the immortal time bias that may be introduced when exposure is defined based on information accrued during follow-up,¹⁴ these patients will be randomly drawn from time-matched vaccination risk sets that are defined as sequential 4-week windows during which they were eligible for inclusion in the RZV cohorts, but without any RZV exposure during the window. Matching within this narrow caliper of calendar time limits the potential immortal time introduced by using future information (ie, lack of RZV receipt) to classify patients at the time of cohort entry. A cohort entry date will be randomly selected from this time window. In addition, other factors, such as duration of tofacitinib use, will be considered for matching upon feasibility, which will be described in the statistical analysis plan (SAP).

To construct the vaccination risk sets, separate 4-week windows will be created, starting on the study initiation date (20 October 2017) through the end of the study period. Among patients who are current tofacitinib users within a given 4-week window, patients without any RZV exposure who meet the study inclusion criteria (Section 9.2.1) and exclusion criteria (Section 9.2.2) at the beginning of the 4-week window will be identified. These patients will be eligible to be sampled as comparator patients for each RZV initiator identified with receipt of a second RZV dose during the same 4-week window. For example, as illustrated in Figure 4, patient A at the time of second RZV dose was eligible to be matched to comparator patient B and D during risk set #1, and similarly, patient B at the time of second RZV dose was eligible to be matched to comparator patient D and E during risk set #2.

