Up to 2 comparators for each RZV initiator will be selected, matched on data source (ie, the Optum Research Database [ORD] or the Optum Medicare Advantage and Medicare Part D [MA-PD] Database) and other factors considered upon feasibility. Patients will be sampled with replacement. This process will be repeated for each 4-week window during the study period; as such, it is possible that a patient could be sampled as a comparator multiple times during the study. If patients are selected more than once into the study, it will be accounted for in the statistical analysis (Section 9.7.3).

Figure 4. Example of Time-Matched Vaccination Risk Sets in the RZV 2-Dose Analysis

If a patient selected for the comparator cohort subsequently receives RZV, their follow-up time within the comparator cohort will be censored upon the date of first administration of RZV. The patient may then be included in the RZV cohorts if they still meet all eligibility criteria. Consequently, patients are eligible to contribute person-time to the RZV cohort, the comparator cohort, or both the comparator cohort and (if subsequently vaccinated) the RZV cohort. Once a person contributes person-time to the RZV cohort, they are no longer eligible to contribute to the comparator cohort.

Patients with and without RZV exposure will be included in the UC RZV cohort and UC Comparator cohort, respectively, if they have at least one medical claim with a diagnosis of UC (International Classification of Diseases, 10th revision [ICD-10] code: K51*) in any position in the 365 days prior to and including their cohort entry date. Similarly, patients with and without RZV exposure will be included in the RA RZV cohort and RA Comparator cohort, respectively, if they have at least one medical claim with a diagnosis of RA (ICD-10 code: M05*) in any position in the 365 days prior to and including their cohort entry date. In addition, M06* (other rheumatoid arthritis) will also be used, except M06.1 (adult-onset Still’s disease) and M06.4 (inflammatory polyarthropathy). If a patient has claims with both UC and RA diagnoses in the 365 days prior to cohort entry, the claim closest to the cohort entry date will be used for cohort assignment.

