As patients that have UC and RA may have different clinical characteristics compared to patients that have only one of the two diseases, the number of patients that have both diagnoses will be quantified. Additionally, a sensitivity analysis will be conducted in which the association between RZV exposure and the primary and secondary outcomes is assessed after excluding patients with both UC and RA from the exposure cohorts.

To assess the effect of prior Zostavax vaccination on subsequent RZV effect, an analysis will be performed where the study population is restricted to patients with at least 5 years of enrollment prior to cohort entry. Within this subset, the analysis will be conducted separately among patients with and without Zostavax vaccination during this baseline 5-year period. The effect of prior Zostavax exposure will be informed by the extent to which the estimate of RZV effect differs according to strata of prior Zostavax exposure.

It is possible that the comparator cohorts could include patients previously vaccinated with RZV more than 365 days earlier. To address this potential exposure misclassification, a sensitivity analysis will be performed, for which the study population will be restricted to patients with enrollment that extends back to 20 October 2017 and who do not have any prior administration of RZV during that time. Finally, a sensitivity analysis will be conducted for HZ in which patients are stratified based on their amount of available follow-up time.

Misclassification of disease flares is possible when using claims-based algorithms (for example, patients may change therapy for reasons other than disease flares), leading to over- or under-estimation of the outcome; thus, alternative definitions will be explored and outlined in the SAP as sensitivity analyses. Specifically, sensitivity analysis will explore using a more conservative definition based on only UC-related surgeries or ER and hospitalizations with UC or RA as the primary diagnosis, as well as evaluating more expansive definitions inclusive of other medications of interest, such as biologics or other JAK inhibitor treatments.

Additional sensitivity analysis may be performed if needed.

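### The main analysis can count patients vaccinated more than 365 days earlier as unvaccinated comparators, and the protocol gives two conflicting dates for checking comparator eligibility

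*Protocol*

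**What the plan says.** **RZV history.** Section 8 frames each comparison against tofacitinib-treated patients who do not receive RZV. The operational rule in Section 9.2.2 excludes for "Receipt of RZV (comparator cohorts only in the RZV 2-Dose analysis) during the 365 days prior to cohort entry". Section 9.7.4 states the consequence: "It is possible that the comparator cohorts could include patients previously vaccinated with RZV more than 365 days earlier". Its remedy is a sensitivity analysis limited to patients enrolled continuously since 20 October 2017 with no RZV in that time. Section 9.2.3.2.1.2 adds one further safeguard: "Once a person contributes person-time to the RZV cohort, they are no longer eligible to contribute to the comparator cohort".

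**Timing of the eligibility check.** Section 9.2.1 opens with "Patients must meet all of the following inclusion criteria at the time of cohort entry" and defines cohort entry by an RZV administration date. Section 9.2.2 counts its look-backs from cohort entry, and the diagnosis look-back in Section 9.2.3.2.1.2 runs to the cohort entry date for patients with and without RZV. The risk-set text in that same section instead selects "patients without any RZV exposure who meet the study inclusion criteria (Section 9.2.1) and exclusion criteria (Section 9.2.2) at the beginning of the 4-week window", and then says "A cohort entry date will be randomly selected from this time window". Comparators must also be "but without any RZV exposure during the window". Section 9.2.3.2.2.2 carries the method over to the ≥1 Dose analysis.

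**The concern.** A patient whose RZV claim is already in the database, but is more than a year old, passes Exclusion 1 and can be sampled as unvaccinated in the main analysis. If that patient keeps some protection, the comparator HZ rate falls and VE is underestimated. Section 9.5 sizes the study on whether VE in tofacitinib users can be shown to lie below 85%, so the error pushes toward the finding of interest.

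On timing, a comparator checked at the window start and entered later has an unscreened interval just before entry. Read literally, HZ, an emergency or inpatient flare, a transplant or the end of tofacitinib treatment in that interval would not remove a comparator, whereas the same event before a vaccinee's entry would. Eligibility would then differ by arm.

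**Working it through.** **1. The plan's own figures.** Inputs from Section 9.5: 1.2 HZ cases per 100 person-years in the unvaccinated, 2:1 comparators, reference VE 85%.
- At 2,000 RZV person-years and VE 66.7%: 0.012 × 2,000 × (1 − 0.667) ≈ 8 vaccinated cases, and 0.012 × 4,000 = 48 comparator cases. A conditional binomial (Jeffreys) interval gives an upper VE bound of 84.96%. Relative reduction: (85 − 66.7)/85 = 21.5%.
- At 4,000 person-years and VE 70.8%: 14 against 96 cases, upper bound 83.8%. One case fewer (13) gives 85.3%. Relative reduction: (85 − 70.8)/85 = 16.7%.

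Both stated cut-offs reproduce. They assume comparators with no vaccine protection.

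**2. Who gets past Exclusion 1.** The safeguard bars only people who have already contributed RZV-cohort person-time. It does not reach:
- patients vaccinated while off tofacitinib, because Section 9.2.3.2.1.1 requires the second dose to fall on treatment and Section 9.2.3.2.2.1 requires the same of the first;
- in the 2-Dose analysis, patients with one dose only, who never enter the 2-Dose RZV cohort. This takes the safeguard as operating within each analysis, which is the natural reading.

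**3. Effect on VE.** Let q be the share of comparator person-time from earlier vaccinees, assumed as protected as the RZV cohort:

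VE observed = 1 − (1 − VE)/(1 − q × VE)

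| q (assumed) | True VE 85% | True VE 70% |
|---|---|---|
| 1% | 1 − 0.15/0.9915 = 84.9% | 1 − 0.30/0.993 = 69.8% |
| 5% | 1 − 0.15/0.9575 = 84.3% | 1 − 0.30/0.965 = 68.9% |
| 10% | 1 − 0.15/0.915 = 83.6% | 1 − 0.30/0.93 = 67.7% |
| 20% | 1 − 0.15/0.83 = 81.9% | 1 − 0.30/0.86 = 65.1% |

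The protocol gives no value for q. If earlier vaccinees keep only half the protection, q × VE halves, so the 10% case gives the 5% row. Against the plan's cut-off, taken as fixed: at q = 10% a true VE of 0.667/(1 − 0.1 × 0.333) = 69.0% would be observed as 66.7%.

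**4. Timing gap.** With a 28-day window and an entry day drawn uniformly (an assumption), the gap is 0 to 27 days, mean 13.5. For the 91-day flare look-back, the unscreened stretch before entry averages 13.5/91 = 15% of its length, and at most 27/91 = 30%.

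Exposure to this differs by analysis. In the 2-Dose analysis, HZ on days 1 to 28 excludes the patient and follow-up starts on day 29 (Sections 9.2.2 and 9.2.5.1), so a gap case matters only if it has no claim in those 28 days and one later. In the ≥1 Dose analysis, HZ is counted from the day after entry and flare from the entry date (Section 9.2.5.2), with one HZ claim sufficient (Section 9.3.5.1). A follow-up claim for a gap event can therefore count as a new outcome there.

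**The case against.** The look-back weakness is disclosed and has its own sensitivity analysis. A fixed look-back treats patients uniformly, whereas using all available history makes its length depend on enrolment. The shift at 5% to 10% contamination is 0.7 to 1.4 points at a true VE of 85%, small beside the roughly 18 points between 66.7% and its upper bound at 2,000 person-years. All of that stands. It limits the size of the problem, but does not justify keeping known vaccinees in the primary comparison.

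It can also be said that the risk-set text already asks for patients without any RZV exposure. If that meant ever, Exclusion 1 would be redundant. The sensitivity analysis adds absence of earlier RZV as a separate condition, which implies that the main analysis does not impose it.

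Some stronger readings are tempting but unsupported:
- *The 812 one-dose patients in Table 1 (2,744 − 1,932) become comparators.* Table 1 requires only any tofacitinib dispensing and any RZV, in any order. To be comparators they must still be enrolled, on tofacitinib, eligible and sampled more than a year after the dose.
- *The sensitivity analysis keeps only 31% of patients.* That is the five-year row of Table 2 (593/1,897). Table 2 spans October 2017 to July 2022, so none of its patients needs five years to reach back to October 2017. Two years is met by 1,296/1,897 = 68% and three by 1,007/1,897 = 53%. The table also describes vaccinees, not comparators.
- *The window-start check lets in patients vaccinated during the window.* RZV within the window is already barred.
- *The timing rule raises comparator rates and masks vaccine-related flares.* Recounted HZ could raise comparator rates, but patients who stopped tofacitinib could lower them. Section 9.3.5.2 requires no dispensing of the same drug in the prior 365 days, so flare treatment in the gap can stop later dispensings from counting.

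**Conclusion.** Two points hold.

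First, the main-analysis comparator group can include patients with a recorded RZV claim more than 365 days old. The bias is toward lower VE, provided those patients keep some protection and are otherwise like the other comparators. It is modest: about 1 to 2 points at q = 5% to 10% for true VE between 70% and 85%, and less with partial or waned protection. The size rests wholly on q, which is not in the protocol. The sensitivity analysis leaves the primary estimate unchanged.

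Second, the protocol contradicts itself on when comparators are assessed, and defines cohort entry by an event comparators do not have. This is an inconsistency to resolve, not a settled rule to check at the window start. It matters mainly for the ≥1 Dose analysis, and the net direction of bias is uncertain.

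**What to change.** **RZV history.** In the main analysis, exclude comparators with any RZV claim in all available data since 20 October 2017, whatever their enrolment length. Apply the same all-available look-back for prior RZV to the RZV ≥1 Dose cohort, which Section 9.2.3.2.2.1 currently screens for 365 days, so that the arms are treated alike. Keep the restriction to patients enrolled since October 2017 as the sensitivity analysis.

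**Timing.** Reconcile Section 9.2.3.2.1.2 with Sections 9.2.1 and 9.2.2. Define cohort entry for comparators as their assigned date and apply every inclusion and exclusion criterion on that date, in both the 2-Dose and ≥1 Dose analyses.

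**Cost.** Wording and programming before analysis. No otherwise eligible patient observed to be unvaccinated is lost through the RZV change. Some comparators will fail the entry-date check and need redrawing from the risk set. Look-back length will vary between patients, and RZV given before enrolment remains unseen, which is why the fully enrolled sensitivity analysis should stay.
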